8.2 ASSESSMENTS DURING TREATMENT

The following assessments will be performed during therapy on Day 1 prior to the start of each cycle, unless otherwise specified. A Cycle is defined as 28 days (prexasertib dosing on Day 1 and 15).

There is a window (**up to 4 calendar days prior to the scheduled time point**) for assessments during the study. Any delay within this window is NOT a deviation. Assessments that are to be done on days when study drug is administered must be done **prior to dosing** as these assessments (CBC, CMP, assessment of response, etc) may determine whether or not drug is administered, or if a dose reduction is necessary, unless otherwise noted.

Note for Cycle 1 only: the prestudy assessments that correspond to assessments below may be used as Cycle 1 assessments as long as they are completed within the 72 hours prior to the patient receiving their first dose of study drug. If more than 72 hours have elapsed since the prestudy assessment, the assessment must be repeated for Cycle 1.

- 1. A brief medical history, to capture events that have occurred since the last cycle. Events that were not captured in the baseline complete medical history should be recorded on the AE page of the CRF.
- 2. A brief physical examination, including vital signs and body weight
- 3. ECOG PS (Appendix III)
- 4. Assessment of concomitant medications
- 5. A CBC with differential and platelet count on Day 1 and Day 15 of every cycle
- 6. A CMP Day 1 and Day 15 of each cycle
- 7. Assessment of magnesium (Mg) and phosphorus (P) Day 1 and Day 15 of each cycle
- 8. HbA1c must be obtained Day 1 and Day 15 of each cycle
- 9. Fasting serum glucose must be obtained Day 1 and Day 15 of each cycle
- 10. A pre-dose ECG (within 10 minutes of beginning prexasertib infusion) must be obtained on Cycle 1 and Cycle 2. Additional ECG may be obtained if clinically indicated.
- 11. A post-dose ECG (within 10 minutes of ending prexasertib infusion) must be obtained on Cycle 1 and Cycle 2. Additional ECG may be obtained if clinically indicated. **NOTE:** it is

- preferred to complete the post-dose ECG upon completion of the prexasertib infusion, but prior to LY3023414 dosing.
- 12. Tumor response by clinical assessment of the patient's disease (ie, by physical examination)
- 13. Radiological assessment of tumors (ie, chest and abdomen CT scan) every 8 weeks or as clinically indicated. The methods used for prestudy assessments should be used throughout the study. If possible, the same equipment should be used each time.
- 14. Assessments of other sites of disease must be performed **only to confirm a CR**.
- 15. Toxicity
- 16. If safely accessible, research biopsies of the same metastatic lesion (or different metastases if the initial metastasis has regressed) may be obtained **any time after the completion of Cycle 2 of the treatment combination, or at the physician's discretion**. If a research biopsy from a patient's metastatic disease cannot be safely obtained, a skin biopsy is permitted.
- 17. Whole blood collection (40 mL) for germline exome sequencing studies any time after the completion of Cycle 2 of the treatment combination, or at the physician's discretion.
- 18. Patient diary assessment of LY3023414 dosing and treatment adverse events

8.3 OFF TREATMENT/END OF TREATMENT ASSESSMENTS

This is a single assessment that will be performed within 30 days \pm 2 days when a patient finishes treatment or goes off treatment because of PD, toxicity that places patients off treatment, if patients achieve a confirmed clinical complete response, or in cases of physician decision or where patient withdraws consent. Patients who withdraw consent may not want any further assessments; however, they should be encouraged to have these final assessments done.

NOTE: End of treatment, or off treatment, is NOT considered off study or withdrawn from the study.

The following evaluations will be performed at this visit:

- 1. A brief medical history should be done to capture events that have occurred since the last cycle. Events that were not captured in the baseline complete medical history should be recorded on the AE page of the CRF.
- 2. A brief physical examination, including vital signs and body weight.
- 3. A CBC with differential and platelet count.
- 4. A CMP
- 5. A serum pregnancy test
- 6. A tumor clinical assessment of the patient's disease (ie, by physical examination)
- 7. A toxicity assessment
- 8. Collection of any outstanding patient diaries

8.4 FOLLOW UP ASSESSMENTS

The duration of patient participation in the study will be a maximum of 18 months, which is counted **from the start of treatment**, provided progressive disease has not occurred. Follow-up visits will be performed **every 3 months for 1 year from the date of last treatment dose**. Only research data will be collected during this time.

Note: Patients who die or withdraw consent are considered **off study** and no further information will be collected.

- 1. Additional therapy
- 2. Date and site of relapse or progression
- 3. Survival status
- 4. Toxicities will be recorded for the first 30 days following the last study treatment.
- 5. Clinical and radiological tumor assessment as per standard of care

8.5 BLOOD SAMPLES FOR EXOME SEQUENCING

Whole blood collection (40 mL) for exome sequencing studies will be obtained at baseline and any time after the completion of Cycle 2 of the treatment combination, or at the physician's discretion

No information that identifies the patient will be given to any of the laboratories that will analyze blood samples. Any material analyzed will be supplied with code number identifiers only, without the patient's name or other identifying information. Access to the database which contains patient identifiers is limited to study investigators and project managers only and is safeguarded by a password protection system. Passwords are not shared. If research findings are published from this study, the research patient will not be identified by name.

8.6 BIOPSIES

Research biopsies will be obtained at the following time points (See Appendix IV for tissue collection and handling):

- A minimum of four 14-gauge needle biopsy cores (or the largest core biopsy deemed safe) may be collected at baseline, prior to the initiation of treatment.
- A minimum of four 14-gauge needle biopsy cores (or the largest core biopsy deemed safe) may be collected any time after the completion of Cycle 2 of the treatment combination, or at the physician's discretion.

Second research biopsies may be obtained from a different metastasis if the initial metastasis has regressed. Tissue biopsies of a patient's metastatic locoregional or pulmonary or hepatic disease will be analyzed by next generation sequencing (NGS) for mutations in DNA repair and PI3K pathways, as well as others. Remaining tissue will be frozen and/or formalin-fixed paraffin embedded (FFPE) for biomarker development.

If a research biopsy from a patient's metastatic disease cannot be safely obtained, a skin biopsy is permitted.

9 SAFETY EVALUATIONS

9.1 ADVERSE EVENTS

All Grade 3 and 4 adverse events (AEs), Grades 1 and 2 alopecia, and all grades of neutropenia will be recorded in the CRF throughout the trial. In addition, all treatment-related Grade 1 and 2 laboratory abnormalities, which are deemed "clinically significant" by the Treating Physician will be documented in the CRF.

Adverse events (AEs) will be recorded throughout the trial. Toxicities and AEs will be graded using the Common Terminology Criteria for Adverse Events (CTCAE) Version 4.0 as linked in Appendix I. The events, and the relationship of each event to treatment, will be assessed by the Treating Physician and recorded on the CRF. Additional information about each event, such as treatment required, eventual outcome, and whether or not therapy had to be interrupted or dosages reduced, will also be recorded on the CRF. Adverse events will be recorded for up to 30 days following the last study treatment.

Definitions and additional reporting instructions are provided in Part II of this protocol.

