6.1.5 Adverse Effects

For LY3023414 monotherapy (N=108), the most common (that is, occurring in \geq 10% of patients) treatment-emergent adverse events (TEAEs) that were considered possibly related to LY3023414 in Study CBBA (N=96) included nausea (36.5%), fatigue (36.5%), vomiting (31.3%), decreased appetite (22.9%), diarrhea (20.8%), rash (13.5%), and oral mucositis (11.5%). Most of these TEAEs were graded as mild or moderate in severity.

LY3023414 monotherapy has been also studied in Asian cancer patients (a Japanese cancer population) in Study CBBH (N=12). The most common (that is, occurring in ≥5 patients) TEAEs that were considered possibly related to LY3023414 in this study included stomatitis (9 patients), nausea (8 patients), decreased appetite (7 patients), and platelet count decreased, anemia, and diarrhea (each 5 patients). Most of these TEAEs were graded as mild or moderate in severity.

The most frequently (that is, occurring in ≥4 patients) reported SAEs regardless of causality within the LY3023414 clinical program included dyspnea (10 patients), nausea and fatigue (each 5 patients), and dehydration, atrial fibrillation, abdominal pain, diarrhea, deep vein thrombosis, and hypotension (each 4 patients). Two deaths were considered due to SAEs (1 case each of pneumonia and pneumonia fungal) which were not related to study treatment. For further details, please refer to the LY3023414 Investigator's Brochure. ²⁶

Pregnancy

Animal reproduction studies have not been conducted with LY3023414. It is not known whether LY3023414 can affect reproductive capacity in humans. There is no clinical trial experience in pregnant individuals. However, based on data from an embryo–fetal developmental study, LY3023414 has the potential for teratogenicity and embryo/fetotoxicity and, therefore, may result in fetal harm when administered to a pregnant woman. LY3023414 must not be given to pregnant women. To minimize any potential risk, pregnant and breastfeeding women must be excluded from clinical trials of LY3023414. Women of childbearing potential should be advised to avoid becoming pregnant during therapy with LY3023414 and should be administered pregnancy tests prior to each cycle of treatment. Investigators should advise men to avoid

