7.3 TOXICITY

Toxicities will be graded according to the NCI Common Terminology Criteria for Adverse Events (CTCAE) Version 4.0 as linked in Appendix I. This document can also be downloaded from the Cancer Therapy Evaluation Program (CTEP) home page http://ctep.cancer.gov. Events must be documented on the AE page of the CRF.

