12.2 REPORTING

12.2.1 Adverse Events

Adverse events will be recorded for the duration of a patient's study treatment, and for up to 30 days following the last study treatment. All AEs, regardless of causal relationship are to be recorded in the source documentation. Only those specified in Section 9.1 are to be recorded in the CRF. The Investigator will attempt to establish a diagnosis of the event based on signs, symptoms, and/or other clinical information. The diagnosis should be documented as the AE/SAE and not the individual signs /symptoms.

Toxicities will be graded according to the NCI Common Terminology Criteria for Adverse Events (CTCAE) Version 4.0 as linked in Appendix I. The event, and the relationship of each event to treatment, will be assessed by the Investigator and recorded on the CRF. Additional information about each event, such as treatment required, whether or not therapy had to be interrupted or dosages reduced, and eventual outcome will also be recorded on the CRF.

Pre-existing conditions will be recorded at baseline on the Medical History Form. If a pre-existing condition does not change, it does not have to be reported as an AE on **subsequent** cycles.

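### Sections 9.1 and 12.2.1 keep non-serious, non-laboratory Grade 1-2 adverse events (except alopecia) out of the CRF, while Sections 7.3, 8.2 and 8.3 send events there with no grade limit

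*Combined protocol and SAP*

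**What the plan says.** The restrictive rule is in two places. Section 9.1 opens with "All Grade 3 and 4 adverse events (AEs), Grades 1 and 2 alopecia, and all grades of neutropenia will be recorded in the CRF", and its next sentence adds treatment-related Grade 1-2 laboratory abnormalities that the treating physician considers clinically significant. Section 12.2.1 separates source from CRF: "All AEs, regardless of causal relationship are to be recorded in the source documentation", but "Only those specified in Section 9.1 are to be recorded in the CRF".

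The unrestricted wording is in four places:
- Section 7.3, after naming the grading system: "Events must be documented on the AE page of the CRF".
- Section 8.2, item 1, on the history taken each cycle: "Events that were not captured in the baseline complete medical history should be recorded on the AE page of the CRF".
- Section 8.3, item 1, which repeats that sentence for the end-of-treatment visit.
- Section 9.1, second paragraph: "The events, and the relationship of each event to treatment, will be assessed by the Treating Physician and recorded on the CRF". It also wants each entry to show whether therapy was interrupted or the dose reduced.

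Two further provisions widen what reaches the AE page. Section 9.2 adds abnormal laboratory results associated with an AE, and Section 12.2.2 adds every SAE. Neither has a grade limit.

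Section 11.1.1 plans AE tables on the Safety Population, with no grade restriction and no named data source. On the common related LY3023414 toxicities, Section 6.1.5 reports: "Most of these TEAEs were graded as mild or moderate in severity".

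**The concern.** A coordinator with a non-serious Grade 2 rash in front of them cannot follow all of these instructions. Section 7.3 requires the event on the AE page; Section 12.2.1 says it does not belong there. Two patients with the same event could be recorded differently.

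Two things are at stake. The first is the safety summary. A table presented as adverse events in the Safety Population, with no grade qualifier, will be read as covering all grades. If it rests on a CRF that leaves out most low-grade events, it understates tolerability problems with a twice-daily oral drug given continuously.

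The second is the link between events and treatment changes. Nonhematologic toxicity above Grade 1 can hold treatment. If the Grade 2 event behind a hold is not on the CRF, the exposure data show an interruption with no recorded cause, although Section 9.1 asks for that connection.

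**Working it through.** The plan gives no figure on this point to reproduce. The check is a comparison of text, followed by an illustration of size.

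**Step 1. What reaches the CRF under the restrictive rule.** Combining 9.1, 9.2, 12.2.1 and 12.2.2:
- Grade 3-4 AEs: yes (9.1).
- Neutropenia and alopecia: yes, including Grades 1-2 (9.1).
- Clinically significant, treatment-related Grade 1-2 laboratory abnormalities: yes (9.1).
- Abnormal laboratory results associated with an AE: yes (9.2).
- SAEs of any grade: yes (12.2.2).
- Non-serious, non-laboratory Grade 1-2 AEs other than alopecia: no.

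Under 7.3, 8.2, 8.3 and the second paragraph of 9.1, read as written, the last group also goes in. The conflict is confined to that group.

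**Step 2. How much expected toxicity falls in that group.** Inputs are the related-event rates for LY3023414 monotherapy in Section 6.1.5 (N=96) and the sample size of 10 in Section 11.3. Expected patients = 10 x rate:
- nausea 3.65
- fatigue 3.65
- vomiting 3.13
- decreased appetite 2.29
- diarrhea 2.08
- rash 1.35
- oral mucositis 1.15

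The sum is 17.3 patient-event pairs. A patient with two of these toxicities counts as two pairs.

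The protocol says only that most of these events were mild or moderate, so the Grade 1-2 share *s* is an assumption, varied from 51% to 100%. Missing pairs = 17.3 x *s*:
- *s* = 51%: 8.8
- *s* = 75%: 13.0
- *s* = 90%: 15.6
- *s* = 100%: 17.3

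The chance that at least one of 10 patients has an unrecorded event of a given type is 1 - (1 - rate x *s*)^10. For nausea at *s* = 51%: 1 - (1 - 0.365 x 0.51)^10 = 0.873; at 100% it is 0.989. For oral mucositis the range is 0.454 to 0.705, and for rash 0.510 to 0.765.

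**Step 3. Events that can hold treatment.** Section 7.2.4 continues either drug only once nonhematologic toxicity has resolved to Grade 1 or baseline. Table 4 delays prexasertib for other nonhematologic toxicity of Grade 2. Footnote b to Table 4 exempts alopecia, fatigue and toxicities that treatment can control, such as nausea, vomiting and diarrhea; Section 7.2.4 states no such exemption. Rash and mucositis are not named in the footnote. Together they account for 1.35 + 1.15 = 2.5 expected pairs of any grade, of which 2.5 x 0.51 = 1.3 up to 2.5 would be Grade 1-2. The protocol does not separate Grade 1 from Grade 2, so the number that would actually hold treatment cannot be calculated.

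**The case against.** The best defense is that the split is deliberate. Section 12.2.1 addresses the exact question, sending all AEs to source and a subset to the CRF, and a specific rule can be read as controlling general statements elsewhere. The sentence in 8.2 and 8.3 mainly separates new events from baseline history. Limiting CRF capture is a legitimate choice in a 10-patient exploratory pilot whose primary objective is response rate and which lists no safety objective. Low-grade events are not destroyed: they stay in source documents and in the Appendix V diary, which lists nausea, vomiting, mouth sores, diarrhea, fatigue, loss of appetite and rash. All of this stands, and it makes requiring every grade closer to a preference. It does not remove the conflicting instructions or explain AE tables with no stated grade limit.

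A reader might also infer several stronger points that the documents do not support:
- *That the CRF holds nothing beyond Grade 3-4 events, alopecia and neutropenia.* Sections 9.1, 9.2 and 12.2.2 add laboratory abnormalities and SAEs, which cover much of the hematologic toxicity expected from prexasertib.
- *That the safety tables will certainly be incomplete.* Section 11.1.1 names no data source. CRF dependence is an inference, supported by Section 13.2.2, which has data entered on the CRF and describes no other route.
- *That all the common low-grade toxicities trigger holds that go unexplained.* Footnote b removes fatigue and controllable gastrointestinal events from the Table 4 delay. Holds for Grade 3-4 events or neutropenia do have a CRF event, and reasons for stopping treatment go on the Change of Status page (Section 4.4).
- *That sites will diverge.* The protocol names one IRB and one tissue core; only the disposition summary in 11.1.3 mentions study sites.
- *That the Grade 1-2 share is known to be high, such as 80-95%.* The protocol gives no figure.

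**Conclusion.** The inconsistency is real and is in the current text. It is limited to non-serious, non-laboratory Grade 1-2 events other than alopecia. Its consequence is conditional: if the 11.1.1 tables come from the CRF under the 12.2.1 rule, then even the lowest reading of *most* leaves out about half of the expected patient-event pairs for the common LY3023414 toxicities, and the highest leaves out all of them.

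The counts rest on three assumptions: monotherapy rates for related events apply to this trial, the Grade 1-2 share lies between 51% and 100%, and none of the low-grade events is serious. Section 1.5 reports higher incidence in combination than with either drug alone, which would raise the counts. That experience led to a recommended prexasertib dose of 105 mg/m², whereas this trial starts at 80 mg/m², so the size of any increase is unknown.

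The gap between events and holds affects some Grade 2 events, with rash and mucositis the clearest examples. This is a correction worth making because it is cheap and improves the safety record. It does not affect the response-rate objective, and it concerns data capture only, not how toxicity should be managed.

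**What to change.** Adopt one CRF rule and state it identically wherever the CRF is mentioned (7.3, 8.2 item 1, 8.3 item 1, both paragraphs of 9.1, and 12.2.1):
- As a minimum, enter all AEs of Grade 2 or higher and any AE of any grade that leads to a delay, dose reduction or discontinuation of either drug. Keep the existing provisions for alopecia, neutropenia, laboratory abnormalities and SAEs.
- Preferably, enter all grades, which removes the conflict completely.
- In 11.1.1, name the CRF as the source of the AE tables if that is the intention. If any grade remains excluded, say so in the table titles, for example that Grade 1 events were not systematically collected.

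The recording window needs no change: 30 days after last treatment is already stated in 9.1, 12 and 12.2.1.

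The cost is data entry. At the monotherapy rates, entering all grades adds roughly 9 to 17 patient-event pairs for the seven common toxicities over the whole trial. It adds more if recurrences are logged separately, and some further entries for other low-grade events. The information is already kept in source documents and diaries, so no new assessment or patient burden is involved.

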9.2 LABORATORY DATA

For the treatment of the patient, laboratory data will be obtained according to the schedule of assessments. Only the laboratory data requested on the CRF need to be recorded on the appropriate laboratory CRF page. In addition, abnormal results that are associated with an AE will be documented on the Adverse Event page of the CRF if the laboratory abnormality fits the definition of an AE or can potentially result in an AE.

10 EFFICACY ASSESSMENTS (SOLID TUMOR)

All efficacy assessments will be investigator assessments of response, time to response, and duration of response. Investigator will determine objective response rate, complete response (CR), partial response (PR), stable disease (SD), or progression of disease (PD).

11 STATISTICAL CONSIDERATIONS

11.1 POPULATIONS FOR ANALYSIS

11.1.1 Analysis Populations

Intent-To-Treat (ITT) Population: Includes all patients registered on the study (eligible and ineligible). This population will be included in overall patient listings, in summary tables of patient demographics and baseline disease characteristics, and also in the list of treatment discontinuations after enrollment.

Evaluable Population: Includes all eligible patients who meet the protocol-specified efficacy analyses requirements and who have received at least 1 dose of study drugs. This population will comprise those patients who will be assessed for pathologic response. Early discontinuation of treatment (in Cycles 1-2), secondary to toxicity, will be considered a treatment failure. If death occurs before the completion of 1 cycle, the patient will be reported as evaluable, early death, but deemed not evaluable for response.

Safety Population: Includes all patients (eligible and ineligible) who receive at least 1 dose of study drugs. This safety population will also be used for the summaries and analysis of all safety parameters (drug exposure, tables of adverse events information, including serious adverse events, etc.). Adverse events that are unrelated to treatment and that occur >30 days after the administration of treatment will not be reported or analyzed.

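### On its ordinary reading, Section 11.1.1 takes Cycle 1 deaths out of the response-rate denominator, which can raise the primary ORR but never lower it

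*Combined protocol and SAP*

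**What the plan says.** The primary objective is the ORR, meaning CR+PR (Section 2.1). Section 11.1.1 defines three populations:

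- **ITT**, all registered patients. Its role is descriptive: "This population will be included in overall patient listings, in summary tables of patient demographics and baseline disease characteristics", plus the list of discontinuations.
- **Safety**, all dosed patients, for safety summaries.
- **Evaluable**: "Includes all eligible patients who meet the protocol-specified efficacy analyses requirements and who have received at least 1 dose of study drugs". Its role is stated as follows: "This population will comprise those patients who will be assessed for pathologic response". Pathologic response is not an endpoint of this trial.

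Two handling rules follow for the Evaluable Population. The first is "Early discontinuation of treatment (in Cycles 1-2), secondary to toxicity, will be considered a treatment failure". The second covers death before the first cycle is finished: "the patient will be reported as evaluable, early death, but deemed not evaluable for response".

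Section 10 leaves the response category to the investigator and gives no denominator. Section 11.4 counts responders out of 10 patients: 0-1 stops enrollment, and 2 or more may lead to 10 more patients. It also sets a benchmark of 30% for responses lasting at least 12 months, again without a denominator.

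**The concern.** The two handling rules treat similar patients differently. Someone who stops early for toxicity stays in as a failure. Someone who dies in the same period is given no response status, and on the ordinary meaning of those words is left out of the response analysis. That exclusion depends on outcome and removes almost only non-responders.

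Section 11.2 calls the trial exploratory and descriptive, so the ORR estimate and its interval are the primary result. Two analysts could compute that estimate differently from the same data. The protocol's own background shows that the choice of denominator is visible in practice. Section 1.4 reports the ovarian cancer study of prexasertib both ways: 8/24 (33%) in assessable patients and 8/28 (29%) by intention to treat. No such pair is planned here.

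**Working it through.** **1. The plan's own figure.** Section 11.4 gives a 60% chance of 4 or more responses in 20 patients at a true rate of 20%. The exact binomial tail is P(X ≥ 4 | n = 20, p = 0.20) = 0.589. The figure reproduces to about one point, and the present point does not affect it.

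**2. Can a Cycle 1 death be a responder?** Section 8.2 sets a 28-day cycle and imaging every 8 weeks (day 56) or as clinically indicated. It also requires, before each cycle, "Tumor response by clinical assessment of the patient's disease (ie, by physical examination"). The first scheduled on-treatment assessment after baseline is therefore the one for Cycle 2. A patient who dies in Cycle 1 would normally have none. An unscheduled scan is possible, so such a patient is almost surely, rather than certainly, a non-responder.

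**3. Direction.** Let x be responders, N treated patients, and k Cycle 1 deaths removed, all non-responders. The change in ORR is

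x/(N − k) − x/N = xk / [N(N − k)].

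This is positive when x ≥ 1 and k ≥ 1, and zero otherwise. For example, 0/10 and 0/9 are both 0%.

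**4. Size**, with exact (Clopper-Pearson) 95% intervals:

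| Responders / treated | Deaths removed | ORR | 95% interval |
|---|---|---|---|
| 2 / 10 | 0 | 2/10 = 20.0% | 2.5% to 55.6% |
| 2 / 10 | 1 | 2/9 = 22.2% | 2.8% to 60.0% |
| 2 / 10 | 2 | 2/8 = 25.0% | 3.2% to 65.1% |
| 4 / 20 | 0 | 4/20 = 20.0% | 5.7% to 43.7% |
| 4 / 20 | 1 | 4/19 = 21.1% | 6.1% to 45.6% |

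The rows for 20 patients apply only if the trial is expanded by amendment.

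**5. How often it would matter.** The documents give no Cycle 1 death rate, so a range is assumed. With a per-patient probability d, the chance of at least one such death in 10 is 1 − (1 − d)^10. If deaths are dropped and the all-treated ORR is 20% (the rate used in Section 11.4), the expected reported ORR is 0.20/(1 − d).

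| Assumed d | Chance of at least one death in 10 | Expected ORR |
|---|---|---|
| 2% | 18% | 20.4% |
| 5% | 40% | 21.1% |
| 10% | 65% | 22.2% |

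**6. Decisions.** The continuation rule counts responders, and removing non-responders leaves that count unchanged. For the 30% benchmark, a count of 2 among 10 would need four exclusions to pass it (2/7 = 28.6%, 2/6 = 33.3%). Moreover, the benchmark concerns responses of at least 12 months, which are only a subset of the responses counted in the ORR.

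**The case against.** The sentence on early deaths need not contradict itself. It can be read as a two-level label: the patient belongs to the Evaluable Population and carries an early-death category for response. On that reading the patient stays in the denominator and there is no bias. Section 11.4 lends support, since it speaks of ten enrolled and treated patients and then counts responses out of 10. This stands as a tenable second reading. It does not settle the matter, because Section 11.4 gives a stopping count and does not define the ORR estimate.

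The practical effect is also modest. Early deaths are to be reported as such, so a reader could recompute the rate. That stands too, and it limits the severity.

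Three stronger inferences are tempting, and the documents do not support them:

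- *That the plan gives the ORR no population at all.* Once pathologic response is taken as a slip for objective response, the Evaluable Population is the implied ORR set. What is unclear is the handling of a subgroup within it.
- *That later deaths or dropouts leave the rate in the same way.* A patient who dies in Cycle 2 would normally have had the clinical tumor assessment due before that cycle, and Section 8.3 requires another when a patient goes off treatment. The entry requirements for the Evaluable Population are not spelled out, but the group with no assessment after baseline should be small.
- *That the continuation rule is weakened.* This would need early deaths to be replaced, or the ten to be read as ten response-evaluable patients. The documents provide for neither.

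**Conclusion.** The point holds as a minor one. On the ordinary reading of Section 11.1.1, Cycle 1 deaths leave the ORR denominator while early toxicity stops remain as failures. The primary ORR is then biased upward if there is at least one such death and at least one responder. With 2 responders among 10, the rise is 2.2 percentage points for one death and 5.0 for two, well inside the sampling uncertainty.

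This rests on two assumptions: that the ordinary reading is the one applied, and that Cycle 1 deaths are non-responders. On the second reading there is no bias, and the defect is only that the text allows both. A reader might infer that the reported ORR will certainly be inflated, or that a go/no-go conclusion could turn on this. Neither follows.

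**What to change.** In Section 11.1.1:

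- Replace the early-death rule. Treated patients who die before completing Cycle 1, or who have no tumor assessment after baseline (clinical or radiological), stay in the primary ORR denominator as non-responders.
- Replace pathologic response with objective response (CR+PR).

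In Section 11.4, state the same denominator for the 30% durable-response rate.

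An ORR that excludes early deaths may be shown as a sensitivity analysis. Whether treated but ineligible patients also enter the primary denominator is a separate choice for the sponsor. It is not needed to mend this point and can be shown as a further sensitivity analysis.

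The cost is a few sentences, with no new data and no change to how response is judged. The reported ORR may be slightly lower. If the change is held to affect study design, Section 13.3 would require a formal amendment with IRB approval, and it could travel with the next amendment.
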